3.2 Analysis Populations

3.2.1 Full Analysis Set (FAS)

The FAS will consist of all subjects who are randomized and receive any study drug. All analyses using the FAS will group subjects according to randomized treatment. The primary endpoint, clinical outcomes/status, survival, and pharmacodynamic endpoints will be analyzed using the FAS. The IA will be based on FAS.

3.2.2 Safety Analysis Set

The Safety Analysis Set is defined as all subjects who receive any study drug. All analyses using the Safety Analysis Set will group subjects according to treatment actually received. The Safety Analysis Set will be used for all safety and tolerability analyses.

3.2.3 Pharmacokinetic (PK)/Pharmacodynamic (PD) Analysis Set

The PK/PD Analysis Set will consist of all the sentinel subjects who receive any study drug.

3.3 Subject Data and Study Conduct

3.3.1 Subject Disposition

Subject disposition will be listed by subject.

The number and percentage of subjects in each of the following categories will be presented by the treatment group and overall for all screened subjects:

- screened,
- randomized,
- treated,
- randomized but not treated,
- completed the Treatment Period, and
- completed the study.

Primary reasons for discontinuation of study treatment and primary reasons for discontinued study will be tabulated.

3.3.2 Protocol Deviations

Any major protocol deviation will be documented as described in the protocol deviation plan, and its impact on inclusion in each analysis population for any subject will be specified. The final list of protocol deviations impacting the analysis populations will be reviewed prior to database lock. Counts and percentages of subjects with major protocol deviations by deviation category will be summarized for all randomized subjects.

3.3.3 Analysis Populations

The numbers and percentages of subjects randomized and included in each analysis population will be tabulated.

3.3.4 Demographic and Baseline Characteristics

The following demographic and baseline characteristics will be summarized:

- Age (years) and age categories (<65 years, \geq 65 years)
- Sex
- Race
- Ethnicity
- Height (cm)
- Weight (kg)
- Body mass index (BMI) (kg/m^2) and BMI categories (<30 kg/m^2 , \geq 30 kg/m^2)
- Requirement for oxygen at randomization (yes, no)
- Chest imaging
- COVID-19 diagnosis
- Baseline CRP by central lab (Day 1) and categories
- Baseline IL-6 by central lab (Day 1)
- Viral load by central lab PCR (Day 1 and Day 7, unless sentinel group or ET)
- Region (US, Ex-US)

Demographic and other baseline characteristics will be summarized using descriptive statistics for the treatment group and overall for all randomized subjects.

3.3.5 Medical History

Medical history terms will be coded using the Medical Dictionary for Regulatory Activities (MedDRA, Version 23.0). Medical history will be summarized by treatment group and overall using coded system organ class and preferred term. In addition, COVID-19 associated medical history which may include diabetes, obesity, chronic kidney disease, hypertension, cancer, cardiac disease, immunocompromised state post-transplant, Chronic obstructive pulmonary disease, and asthma will be summarized separately. Medical history will also be listed.

3.3.6 Prior and Concomitant Medications

Prior medications will include medications which started prior to the first dose of study drug.

Concomitant medications will include medications or non-medication therapeutic agents (convalescent plasma therapy for example) taken on and after the first dose of study drug.

Medications that started prior to the first dose of study drug but continued into treatment are considered as both prior and concomitant.

All medications will be coded using the World Health Organization Drug Dictionary (WHO Drug Global B3, March 2020). A frequency table of the number and percentage of subjects will be provided for concomitant medications by therapeutic class and preferred name for the Safety Analysis Set. Prior and concomitant medications will be summarized separately.

Prior and concomitant medications will be also listed by international nonproprietary names, dose, regimen, route and for which indication it was prescribed.

3.3.7 Concomitant Procedures/Non-Drug Therapies

Concomitant procedures and non-drug therapies will be listed.

3.3.8 Study Drug Exposure and Compliance

Exposure to study treatment will be described in terms of duration of treatment. Exposure in days is defined as the date of last dose of study drug minus the date of first dose of study drug plus 1. Exposure in days will be summarized. In addition, a contingency table will be provided to display the number and percentage of subjects with exposure in the following categories:

- <1 week (<7 days),
- >=1 - <=2 weeks (7 - 14 days),
- >2 weeks (>14 days).

Treatment compliance will be calculated as (the number of tablets dispensed - the number of tablets returned) divided by (the number of tablets expected to be taken during the Treatment Period, calculated as four tablets daily times 14 days). Percent compliance will be summarized. In addition, the number and percentage of subjects within each treatment group with overall compliance in the following categories: <80%, 80% to 120%, and >120%, will be provided for the Safety Analysis Set.

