5 INVESTIGATIONAL MEDICINAL PRODUCT

5.1 Investigational drug and matching placebo

Losmapimod will be provided in tablets of 7.5 mg for oral administration.

Matching placebo tablets will be provided for oral administration.

The tablets are plain white, round, biconvex, film-coated tablets. The proposed dosing regimen is as a twice daily dose of 15 mg (2 x 7.5 mg tablets/dose BID). The proposed duration of treatment is for up to 14 days.

Subjects should take their dose of losmapimod or placebo with food whenever possible and with 240 mL of room temperature water.

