2.2.3 Study Drug

Losmapimod will be provided in tablets of 7.5 mg for oral administration.

Matching placebo tablets will be provided for oral administration.

The tablets are plain white, round, biconvex, film-coated tablets. The proposed dosing regimen is as a twice daily dose of 15 mg (2 \times 7.5 mg tablets/dose BID). The proposed duration of treatment is for up to 14 days.

Subjects should take their dose of losmapimod or placebo with food whenever possible and with 240 mL of room temperature water.

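### Compliance is divided by a fixed 56 tablets, so a subject who took every dose but stopped by Day 11 and returned the rest is tabulated as under 80% compliant

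*SAP*

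**What the plan says.** SAP 3.3.8 takes tablets handed out less tablets handed back and divides by the tablets expected over the treatment period, "calculated as four tablets daily times 14 days". The result is summarised as a percentage and in bands, in that counts of subjects with "overall compliance in the following categories: <80%, 80% to 120%, and >120%, will be provided for the Safety Analysis Set". SAP 3.2.2 puts everyone who took any study drug in that set, so early stoppers and deaths are included.

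The four tablets a day come from Protocol 5.1, "twice daily dose of 15 mg (2 x 7.5 mg tablets/dose BID". On length, SAP 2.2.3 says "The proposed duration of treatment is for up to 14 days", so 14 days is a maximum.

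SAP 3.3.8 also derives each subject's actual time on drug: "Exposure in days is defined as the date of last dose of study drug minus the date of first dose of study drug plus 1". It plans an exposure row for "<1 week (<7 days", so it foresees early stopping, but the compliance denominator does not use this quantity. Nothing elsewhere changes the formula. Protocol 8.5.4 covers duration only, Protocol 5.4.3 covers bottle review and collection, and the SAP's list of changes from the protocol (section 6) does not mention compliance.

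**The concern.** A compliance percentage should show how much of the drug that was due a subject actually took. After death, or after study drug has been permanently stopped, nothing more is due. Protocol 3.4.1 obliges the investigator to stop drug in some circumstances, and Protocol 7.1.8 directs stopping for subjects who meet its QTc or liver criteria. A subject whose drug was stopped under those sections, with no dose missed beforehand, is tabulated beside subjects who skipped doses.

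What is at stake is how one descriptive table is read. The under-80% row would hold two different groups, and someone asking whether the assigned regimen was taken could not separate them from that row alone.

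**Working it through.** **Inputs.** Tablet strength 7.5 mg and dose 15 mg twice daily (Protocol 5.1); 14 days, tablets used, and the 80% and 120% cut-offs (SAP 3.3.8); Day 1 is the day of first dose (SAP 3.1.1).

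**The plan's own figure.** Tablets per day = (15 / 7.5) × 2 = 4. Expected tablets = 4 × 14 = 56. The SAP states the product without printing 56.

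**Cut-offs in tablets.** 80% of 56 = 44.8 tablets, or 44.8 / 4 = 11.2 full dosing days. 120% of 56 = 67.2 tablets.

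**Score for a subject who misses nothing.** If four tablets are taken on each of Days 1 to d and the rest are returned and counted, the SAP score is 4d/56. With expected tablets limited to days on drug, it is 4d/4d.

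| Last dosing day d | Tablets taken | SAP score | SAP band | Score with 4d expected |
|---|---|---|---|---|
| 1 | 4 | 7.1% | <80% | 100% |
| 4 | 16 | 28.6% | <80% | 100% |
| 7 | 28 | 50.0% | <80% | 100% |
| 10 | 40 | 71.4% | <80% | 100% |
| 11 | 44 | 78.6% | <80% | 100% |
| 12 | 48 | 85.7% | 80–120% | 100% |
| 13 | 52 | 92.9% | 80–120% | 100% |
| 14 | 56 | 100.0% | 80–120% | 100% |

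The band is wrong through Day 11 and right from Day 12. This counts whole days; a first or last day with only one dose removes two tablets and can move the boundary slightly (44 tablets give 78.6%, 46 give 82.1%).

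**Why the ratio is ambiguous.** A subject who stopped at Day 7 with no missed dose and a subject on drug for 14 days who took half the tablets both used 28, and both score 28/56 = 50.0%. With the denominator limited to days on drug they score 28/28 = 100% and 28/56 = 50.0%.

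**Dependence on returned tablets.** The documents do not say how many tablets are dispensed. Assume 56. If a subject dies on Day 7 and the bottle is never returned, the SAP formula gives (56 − 0)/56 = 100%. Shortening the denominator alone would give 56/28 = 200%, in the >120% band. A rule for uncounted bottles is therefore needed with any change to the denominator.

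**The case against.** The strongest reply is that the SAP states its denominator openly, and that the share of a planned 14-day course actually taken is a coherent descriptive measure. That is fair, but the SAP labels it compliance and bands it at 80%, which invites a reading about adherence.

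Second, nothing inferential depends on it. Compliance defines none of the analysis populations in SAP 3.2, enters no efficacy model in SAP 3.4 and plays no part in the interim rules in SAP 5.1. The report will also show exposure categories, reasons for stopping treatment, and adverse events leading to death or to stopping drug, so a careful reader can partly reconstruct what happened. This stands, and it makes the point minor.

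Third, handling of unreturned bottles may sit in the separate programming specifications (SAP section 7), which are not available here. That may be so, but the fixed denominator is in the SAP itself.

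A reader might also infer three stronger things that the documents do not support:

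- *That early stopping will be common because about 30% are expected to progress.* That figure (Protocol 8.1.1, SAP 2.2.4) is the assumed placebo rate of death or respiratory failure by Day 28. It is not a rate of stopping drug by Day 11, and respiratory failure is not among the listed triggers for stopping drug in Protocol 3.4.1.
- *That the arm with more deaths will look less compliant.* The direction depends on leftover tablets being returned and counted. Bottles are collected at Day 14 or at an early termination visit; neither document says what happens after a death.
- *That the formula measures duration and not compliance.* For a subject on drug for the full 14 days it is an ordinary tablet count and detects skipped doses, which the exposure calculation cannot.

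**Conclusion.** The point holds in a limited form. The stated rule gives a misleading figure for a definable group: subjects who took every dose, whose study drug ended by Day 11 through death or permanent discontinuation, and whose unused tablets were returned and counted. They are reported at 7.1% to 78.6%, all in the under-80% band. Those stopping on Day 12 or 13 score 85.7% or 92.9%, which understates adherence but leaves the band correct.

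This rests on four tablets being taken on each day up to the last and on complete returns. Without returns, the error can run the other way. The number of subjects affected and any imbalance between arms cannot be computed, because no rate of early stopping is given. The consequence is limited to the compliance table; no efficacy or interim conclusion changes. It is worth correcting because it is cheap.

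**What to change.** In SAP 3.3.8, define expected tablets as four times the number of days from first dose to the earliest of Day 14, death, or recorded permanent discontinuation of study drug. Doses skipped before that date still count against the subject.

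Add that compliance is missing when the bottle is not returned or counted, so that an uncounted supply is not scored as 100% or more. Show the number missing in each arm beside the bands.

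If the 56-tablet ratio is still wanted, report it on a separate line as *percent of planned course taken*. Leave the exposure table as it is.

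The cost is two SAP sentences and one derivation, plus missing compliance values for some subjects. The protocol has no compliance formula, so none needs amending.

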3.4 Efficacy Assessment

3.4.1 Primary Efficacy Endpoint

3.4.1.1 Primary Analysis

The primary efficacy endpoint is the proportion of subjects who progress to death or respiratory failure by Day 28.

Respiratory failure is defined as either need for mechanical ventilation (invasive or non-invasive) or high flow oxygen (defined by greater than 15 LPM flow of oxygen to maintain oxygen saturation between 90% and 95%), sustained for at least 48 hours, at any time during the study.

The fitted logistic regression model is used to predict the response rate for every subject in the study as if they had received the treatment or the control intervention.

Assuming p_t is probability of outcome in the losmapimod arm; p_c is the probability of outcome in the control arm

Study hypothesis: $H_0: p_t - p_c = 0$

$H_1: p_t - p_c < 0$

Assuming $p_t=0.18$, $p_c=0.30$, we can restate the hypothesis as

$H_0: \theta = \theta_0 = 0$

$H_1: \theta = \theta_1 = -0.12$

where θ is calculated as $p_t - p_c$. For the final analysis, the proportion of subjects achieving the primary endpoint in the treatment arms will be compared using an adjusted risk difference obtained from the logistic regression model, adjusted for stratification factors, sex, and baseline CRP. Sample SAS codes are provided in Appendix A. More details can be found in Guo et al. (2012) and Ge et al. (2011).

An interim analysis to assess futility analysis—and potential sample size re-estimation—will be conducted, as discussed in Section 5.1.

All results will be summarized descriptively by treatment arm and expressed as proportions, along with corresponding unadjusted/adjusted 95% CI of the difference between response rates, and p-values.

In the first step of multiple imputation, data will be multiple imputed using the FCS discriminant function separately by treatment arm to 20 imputed datasets. This analysis assumes data are missing at random. The imputation model will include the stratification factors, sex, baseline CRP, and a two-level binary factor (discharge from the hospital prior to discontinuing the study; Yes, No). [REDACTED]

For each imputed dataset, the proportion of subjects achieving the primary endpoint in the treatment arms will be compared using an adjusted risk difference obtained from the logistic regression model, adjusted for stratification factors, sex, and baseline CRP for each imputed dataset.

The estimated treatment effect and associated standard errors from each imputation from the 20 logistic regression model will be combined using Rubin's rules to provide an overall treatment effect, associated 95% confidence interval (CI), and 2-sided p-value. Sample codes are listed below.

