2.2.4 Sample Size Determination

The primary efficacy endpoint of this study is the proportion of subjects who progress to death or respiratory failure by the end of study (Day 28). It is estimated that approximately 30% of enrolled subjects receiving SOC plus placebo will attain this endpoint. It is assumed that losmapimod will improve the primary endpoint by 40% over placebo. On the basis of these assumptions, a total of up to 410 subjects randomized to the losmapimod arm or the placebo arm in a 1:1 ratio (205 subjects in the losmapimod arm and 205 subjects in the placebo arm) will yield approximately 80% power in a 1-sided test at the 2.5% significance level.

The sample size estimate assumes an IA will be conducted after approximately 206 subjects (103 in the losmapimod arm, and 103 in the placebo arm) have completed the Day 28 visit, to assess early futility, using the rules specified in Section 5.1.

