3.1.8 Handling of Dropouts and Missing Data

All missing or incomplete safety and PD data, including dates and times, will be treated as such. Missing test results or assessments will not be imputed, and as such, are assumed missing completely-at-random (MCAR).

For laboratory data, values below the limit of quantitation (recorded as “< LLQ”) will be set to half that limit.

For the analysis of hospital-free and ICU-free days, subjects who die prior to the analysis time point will have post-death days considered to be not hospital-free and not ICU-free.

Adverse events with missing start dates will be considered as treatment-emergent unless the partial date excludes that possibility, e.g., the adverse event month is prior to the first dose of study drug. Otherwise, the first day of the month will be used to impute missing start days and January will be used to impute missing start months. For example, if the first dose of study drug was on January 8, 2021 and an adverse event started in January 2021 with missing day, the start date will be imputed as the first dose date (January 8, 2021) and this adverse event will be considered as treatment-emergent. In the same example, if another adverse event has start month of December 2020 with missing day (before the first dose date of January 8, 2021), its start date will be imputed as December 1, 2020 and will not be considered as treatment-emergent.

Subjects who terminate the study prior to the analysis time point, not due to death, will be considered as missing for the analysis of key efficacy endpoints. Missing data in each treatment arm will be imputed using the observed data in their respective arm under the missing at random (MAR) assumption. Multiple imputation (MI) will be performed using the fully conditional specification (FCS) model. The imputation model will include the stratification factors, sex, and baseline CRP.

The handling of missing data for the key efficacy endpoints are outlined as the following:

1. Primary endpoint: patients whose status could not be ascertained (lost-to-follow up, etc.) will be imputed using multiple imputation approach.
2. Change in Clinical Status at Days 7 and 14: missing clinical status at the post-baseline timepoint will be imputed using multiple imputation approach.

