3.4.2 Secondary Efficacy Endpoints

Clinical status at Day 7 and Day 14:

Change in clinical status between baseline and at Days 7 and 14 will be modeled using ordinal logistic regression models, adjusting for stratification factors, sex and baseline CRP. If the subject progresses to death and the value of WHO 9-point scale is missing, the missing value of WHO 9-point will be imputed as (8) death.

Percentages for each category of the ranking scale will be tabulated by treatment arm, along with differences between treatment arms at each time point. The proportion of subjects for each of the items in the scale will be compared using an adjusted risk difference obtained from an ordinal logistic regression model, adjusting for stratification factors, sex and baseline CRP.

Total number of study days by Day 28:

(a) Free of oxygen supplementation; (b) in ICU; (c) of hospitalization; (d) free of respiratory failure; (e) alive; For each endpoint (a) – (e), a Poisson regression model will be used to assess

the relationship with treatment, adjusting for stratification factors, sex, baseline CRP and number of days on study. The key study endpoint of “oxygen free days by Day 28” will be tested at 1-sided significance level of 0.025 as outlined in Section 3.1.5.

If a patient died, the number of days of (a)-(e) are considered as having the events on and after the patient died. For example, if a patient died on Day 6. The days from Day 6 and after are considered not free of oxygen supplementation, hospitalization, ICU, and respiratory failure.

Percentage of subjects discharged from the hospital by Day 28:

Percentages of subjects discharged from the hospital will be tabulated by treatment arm, along with differences between treatment arms. The proportion of subjects will be compared using an adjusted risk difference obtained from a logistic regression model, adjusting for stratification factors, sex, and baseline CRP.

The percentage of subjects discharged from the hospital is defined as the number of subjects discharged from the hospital divided by the sum of the number of subjects who completed the study and the number of subjects who died during the study period.

A sensitivity analysis will be performed by excluding the subjects who died after being discharged from the hospital from the numerator of the above percentage calculation.

Missing data will be imputed similarly as primary endpoint for the above endpoints.

All-cause mortality at Day 28:

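### The discharge flag in the primary-endpoint imputation is fixed on the withdrawal day for dropouts but, on its natural coding, spans all 28 days for subjects with known outcome, so early in-hospital withdrawals are imputed at too high an event risk

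*SAP*

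**What the plan says.** SAP 3.4.1.1 defines the outcome: "The primary efficacy endpoint is the proportion of subjects who progress to death or respiratory failure by Day 28". Missing outcomes are imputed 20 times under missing at random, separately by arm, with an FCS discriminant function. The predictors are the stratification factors, sex, baseline CRP and "a two-level binary factor (discharge from the hospital prior to discontinuing the study; Yes, No". A redacted stretch follows directly.

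SAP 3.1.8 also describes the imputation for the key efficacy endpoints, the primary among them: "The imputation model will include the stratification factors, sex, and baseline CRP". The discharge flag is not in that list.

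SAP 3.4.2, after the endpoints that end with percentage discharged by Day 28, adds: "Missing data will be imputed similarly as primary endpoint for the above endpoints". The same section takes as the denominator of that percentage the subjects who completed the study plus those who died.

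SAP 2.2.1 expects first-week visits to take place in hospital. Table 1 of Protocol version 3.0 schedules the WHO clinical status daily on Days 1 to 8 and then on Days 10, 12, 14, 21 and 28.

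**The concern.** The imputation model is fitted to subjects whose outcome is known and applied to those whose outcome is not. A predictor has to mean the same thing in both groups. For a subject who leaves the study on Day 3, the flag only records that discharge had not happened by Day 3, which is true of nearly everyone at that point. A subject with known outcome carries a single value. If that value is discharge by Day 28, No means died in hospital or was still there after four weeks. The early withdrawal is then given the prognosis of that much sicker group.

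The mismatch would arise even if withdrawal were completely random, because it comes from the predictor and not from who drops out. At stake is the primary outcome of every early in-hospital withdrawal and, if the arms lose such subjects unequally, the primary risk difference.

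**Working it through.** **The plan's own figure.** Inputs from SAP 2.2.4: a placebo event rate of about 30%; for the effect, "It is assumed that losmapimod will improve the primary endpoint by 40% over placebo"; and for the size, "205 subjects in the losmapimod arm and 205 subjects in the placebo arm". So the rates are 0.30 and 0.18, the difference is -0.12 and the pooled rate is 0.24. With pooled variance under the null:

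n per arm = (1.960·√(2·0.24·0.76) + 0.842·√(0.18·0.82 + 0.30·0.70))² / 0.12² = 197.7, so 198.

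Power at 205 per arm is 0.814 for a fixed design. With the SAP 5.1 boundaries (interim Z -0.67873, final Z -1.91358), one-sided alpha is 0.0250, power is 0.80 and the chance of stopping at the interim under the null is 0.751. The plan's 410 therefore reproduces, and -0.12 is the scale against which to judge a bias.

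**Event rate among subjects never discharged by Day 28.** The documents give no discharge rates, so four pairs are assumed: d_e for subjects with an event and d_n for those without. With p the arm's event rate,

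r_No = p(1 - d_e) / [p(1 - d_e) + (1 - p)(1 - d_n)].

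| d_e / d_n | placebo, p = 0.30 | losmapimod, p = 0.18 |
|---|---|---|
| 0.30 / 0.98 | 0.210/0.224 = 93.8% | 0.126/0.1424 = 88.5% |
| 0.45 / 0.95 | 0.165/0.200 = 82.5% | 0.099/0.140 = 70.7% |
| 0.60 / 0.90 | 0.120/0.190 = 63.2% | 0.072/0.154 = 46.8% |
| 0.60 / 0.85 | 0.120/0.225 = 53.3% | 0.072/0.195 = 36.9% |

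**True risk of the withdrawal.** For a subject in hospital and event-free who leaves on Days 2 to 7, an illustrative simulation gives about 25% on placebo and 15% on losmapimod. Under other timing assumptions it is 16% to 30% and 9% to 18%.

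**Shift in the arm rates and the risk difference.** If a fraction f of an arm withdraws this way, its rate rises by f(r_No - r_true). The risk difference shifts by f_t(r_No,t - 0.15) - f_c(r_No,c - 0.25).

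- 5% in each arm: the placebo rate rises 1.4 to 3.4 points and the losmapimod rate 1.1 to 3.7. The difference moves by -0.3 to +0.2 points.
- 8% on losmapimod, 4% on placebo: second row, 0.08(0.707 - 0.15) - 0.04(0.825 - 0.25) = +2.2 points. Across the four rows it is +0.6 to +3.1, or 5% to 26% of the planned difference. Simulating the true risk instead of fixing it gives +0.7 to +3.1.
- 4% on losmapimod, 8% on placebo: -1.4 to -2.6 points, in favour of losmapimod.

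**Running a discriminant-function imputation.** This was simulated at 205 per arm, with 200 replicates per scenario and Day 3 withdrawals, under four other sets of assumed event and discharge times. The flag led to imputed risks of 0.96 to 1.00. Equal withdrawal of 5% to 10% pulled the difference towards zero by 0.3 to 1.4 points relative to a time-aligned imputation. Withdrawal of 8% v 3% with no true effect produced a difference of 3.3 to 4.1 points against the arm losing more. Donors aligned to the same day recovered the full-data difference to within about 0.002. These timing assumptions make the undischarged group almost all events, so the sizes are nearer an upper case.

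**The case against.** **The coding is inferred.** The redacted text, or sample code that is not in the public copy, may define the flag for subjects who stay. That stands, and the imputed risks above are conditional on the natural coding. If everyone who did not discontinue were coded No, the Yes level would have almost no observed outcomes; the bias would not follow, but the flag could not be estimated. No hidden definition can make one value per completer match withdrawal days that vary between subjects.

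**Such withdrawals should be few.** Protocol 3.4.2 keeps subjects in follow-up after they stop treatment, and declares loss to follow-up only after two contact attempts, a certified letter and 30 days without reply. SAP 3.1.8 imputes only where status could not be ascertained. For dropouts after discharge, separating them from those still in hospital is a sensible aim. All of this stands and limits the size.

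**Stronger readings that a reader might infer.**

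- That most undischarged subjects had the event: one assumed row gives 37% on losmapimod.
- That the primary test has an inflated error rate, or is tilted against losmapimod: the documents give no withdrawal rate and no imbalance, and the direction depends on which arm loses more.
- That SAP 3.1.8 and 3.4.1.1 flatly contradict each other: the first can be read as a general list to which the second adds a term. They still need reconciling.
- That every undischarged withdrawal is imputed as never discharged for the discharge endpoint: SAP 3.4.2 says only that the method is similar, and its denominator leaves these subjects out. What does follow is that the denominator and the imputation sentence do not fit together.

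**Conclusion.** The concern holds as a conditional one. On the natural coding of the flag, early withdrawals who are in hospital and event-free are imputed well above their true risk: 53% to 94% against about 25% on placebo, and 37% to 88% against about 15% on losmapimod. These are approximate, because the imputation also uses baseline covariates. With few or balanced withdrawals the primary result changes little. An 8% v 4% imbalance would move the risk difference by about 0.6 to 3.1 points against losmapimod if that arm loses more, and by about 1.4 to 2.6 points in its favour if placebo does. Discharge rates, withdrawal rates and event timing are all assumptions.

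This is more than an undefined term. A single flag fixed at withdrawal cannot be aligned with completers on any coding, and data already scheduled allow a predictor that can. The change should be made before unblinding, but the documents do not show that the primary analysis is materially biased.

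**What to change.** Replace the flag in SAP 3.4.1.1 with a time-aligned predictor: WHO hospital and oxygen status on the subject's last observed study day. Draw donors from subjects in the same arm who were event-free and in the same status on that same day, and keep the stratification factors, sex and baseline CRP. Use every scheduled day, including Days 1 to 8; a grid of Days 7, 14, 21 and 28 has no post-baseline status for a Day 3 withdrawal. Impute the Day 28 event itself and do not derive it from WHO scores, because respiratory failure must last at least 48 hours and can occur between visits.

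State this one model in both 3.1.8 and 3.4.1.1. For percentage discharged by Day 28, do not use whole-study discharge as a predictor, and decide whether withdrawals are imputed or left out of the denominator.

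The cost is SAP wording and programming; no new data are needed. The imputation model becomes somewhat larger and may need collapsed status categories, since SAP 3.1.7 already plans for non-convergence with sparse data.
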